### 7.1.3 Definition of TB-IRIS

We will use the Meintjes et. al. definition of paradoxical and unmasking TB-IRIS.

#### Paradoxical TB IRIS

##### (A) Antecedent requirements

Both of the two following requirements must be met:

- Diagnosis of tuberculosis: the tuberculosis diagnosis was made before starting ART and this should fulfil WHO criteria for diagnosis of smear-positive pulmonary tuberculosis, smear-negative pulmonary tuberculosis, or extra-pulmonary tuberculosis
- Initial response to tuberculosis treatment: the patient's condition should have stabilised or improved on appropriate tuberculosis treatment before ART initiation—e.g., cessation of night sweats, fevers, cough, and weight loss. (Note: this does not apply to patients starting ART within 2 weeks of starting tuberculosis treatment since insufficient time may have elapsed for a clinical response to be reported)

##### (B) Clinical criteria

The onset of tuberculosis-associated IRIS manifestations should be within 3 months of ART initiation, re-initiation, or regimen change because of treatment failure. Of the following, at least one major criterion or two minor clinical criteria are required:

###### Major criteria

- New or enlarging lymph nodes, cold abscesses, or other focal tissue involvement—e.g., tuberculous arthritis
- New or worsening radiological features of tuberculosis (found by chest radiography, abdominal ultrasonography, CT, or MRI)
- New or worsening CNS tuberculosis (meningitis or focal neurological deficit—e.g., caused by tuberculoma)
- New or worsening serositis (pleural effusion, ascites, or pericardial effusion)

###### Minor criteria

- New or worsening constitutional symptoms such as fever, night sweats, or weight loss
- New or worsening respiratory symptoms such as cough, dyspnea, or stridor
- New or worsening abdominal pain accompanied by peritonitis, hepatomegaly, splenomegaly, or abdominal adenopathy

##### (C) Alternative explanations for clinical deterioration must be excluded if possible

- Failure of tuberculosis treatment because of tuberculosis drug resistance
- Poor adherence to tuberculosis treatment
- Another opportunistic infection or neoplasm (it is particularly important to exclude an alternative diagnosis in patients with smear-negative pulmonary tuberculosis and extrapulmonary tuberculosis where the initial tuberculosis diagnosis has not been microbiologically confirmed)
- Drug toxicity or reaction

#### Unmasking tuberculosis-associated IRIS

Patient is not receiving treatment for tuberculosis when ART is initiated and then presents with active tuberculosis within 3 months of starting ART

AND one of the following criteria must be met:

- Heightened intensity of clinical manifestations, particularly if there is evidence of a marked inflammatory component to the presentation. Examples include tuberculosis lymphadenitis or tuberculosis abscesses with prominent acute inflammatory features, presentation with pulmonary tuberculosis that is complicated by respiratory failure due to adult respiratory distress syndrome, and those who present with a marked systemic inflammatory syndrome related to tuberculosis.
- Once established on tuberculosis treatment, a clinical course that is complicated by a paradoxical reaction

The study team will gather as much information as possible about all possible AESIs. Information will be gathered about TB diagnoses, timing of ART initiation (relative to TB diagnosis and treatment), clinical course (including documentation of relevant diagnostic and therapeutic activities by routine clinical staff), and alternative explanations for clinical symptoms. This information (including judgement of study physician, National PI or delegate) will be presented to an independent expert clinical committee for adjudication about likelihood that symptoms are consistent with TB-IRIS. The adjudication committee will be blinded to arm allocation.

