#### 4.2.2 Blinding

It is not feasible to blind participants and site investigators to arm allocation. However, we do not believe this will influence our aim of conducting a pragmatic trial evaluating the strategies of “ART first” versus “TB results first”.

For endpoint assessment, laboratory staff processing viral load samples will be blinded to arm allocation. Endpoints of death or loss to follow-up will be ascertained by site investigators and therefore not

blinded. For the endpoint assessment of AESI incidence, an expert panel will review clinical data, blinded to arm allocation.

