### 6.2 Randomization (study staff)

Stratified randomization will be performed as outlined in section 4.2.1. Allocation will be revealed to study staff electronically on the study tablet. Study staff will inform routine staff about arm allocation.

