the follow-up period. The periods for which the registers have been reviewed will be documented by the site investigators to avoid double-entries or skipping of time periods. Site investigators must analyze all entries made in the registers during the follow-up period and they must document all possible SAEs and AESIs encountered into the trial database. Site investigators may document visits without occurrence of a possible SAE or AESI, however documentation of uncomplicated visits is not mandatory. The study staff's main responsibility during the follow-up period is the assessment and documentation of possible SAEs and AESIs. In case a participant is referred directly to the study staff, the site investigators will perform a brief medical history, a targeted physical examination and document results together with information about diagnostic investigations and prescriptions by routine staff in the trial database. For events notified to the study staff after the participant has left the study clinic or for events detected during the review of routine registers, the site investigators will capture as much information as possible about the event from clinical routine registers, inquiry of responsible routine staff and via phone calls to participants or relatives if required. If site investigators detect a possible SAE or AESI, the study physician or National PI will be informed by the site investigators. The study physician or National PI will assess the data provided by the site investigators and decide whether further assessment and documentation of the case is required. Possible further documentation may be conducted by the study physician or National PI him- or herself or may be delegated to other qualified study staff including the site investigators after reception of instructions for appropriate documentation of the case. All information captured by the study physician or National PI or her/his delegate will be saved in the electronic trial database together with the information captured previously by the site investigators and will later be used for notification to the Sponsor-Investigator and IECs in case of SAEs or for the assessment by the clinical expert committee for classification in case of possible AESIs.

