### 11.2 Evaluation of the risk-benefit ratio

The group-specific timing for ART initiation relative to TB investigations has the following risks and benefits: In the “ART first” arm, the risk of IRIS is increased due to the earlier initiation of ART whereas the risk of pre-ART attrition from care and thereby of AIDS-related complications, is minimized and the opposite is true for the “TB results first” arm. For an in-depth risk-benefit assessment, we refer to the current WHO HIV guidelines and the systematic review conducted to inform them on the question of when ART should be initiated in PLHIV with presumptive TB. The rationale for the conduction of this trial is that based on the current evidence it remains unclear which of the strategies entails a more favorable overall risk-benefit profile.

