## Safety endpoints

Definitions of SAEs, and AESIs are provided below.

The study team will gather as much information as possible about all possible SAEs and AESIs. Information will be gathered about TB diagnoses, timing of ART initiation

(relative to TB diagnosis and treatment), clinical course (including documentation of relevant diagnostic and therapeutic activities by routine clinical staff), and alternative explanations for clinical symptoms. This information is a narrative clinical report compiled by the study physician using all available information from facility records, staff, patient and relatives and including judgment of study physician, National PI or delegate. Events possibly linked to TB-IRIS were presented to an independent expert clinical committee for adjudication about likelihood that symptoms are consistent with TB-IRIS. The adjudication committee will be blinded to arm allocation.

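### Arm-aware staff decide which events count as possible TB-IRIS before the blinded committee sees them, so the descriptive AESI comparison can be biased even if adjudication is perfect

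*Protocol*

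**What the plan says.** The trial is open-label. Protocol 4.2.2 states "It is not feasible to blind participants and site investigators to arm allocation", and 6.2 adds "Study staff will inform routine staff about arm allocation". The blinding safeguard for TB-IRIS sits at the last step: "For the endpoint assessment of AESI incidence, an expert panel will review clinical data, blinded to arm allocation" (4.2.2). Protocol 7.1.3 and SAP 6.1 also describe the committee as blinded.

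Before that step, an event passes through the following:

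- **Routine staff** are trained to recognise possible SAEs and AESIs and refer participants when they suspect one (Protocol 6.8).
- **Site investigators** must read all register entries for the follow-up period and enter what they regard as a possible SAE or AESI. Visits without such an event may be entered but need not be (6.8).
- **The study physician or National PI** is informed of detected cases and will "decide whether further assessment and documentation of the case is required" (6.8). The documents do not say whether this role is blinded.
- **The committee** receives the material. Protocol 7.1.3 states "The study team will gather as much information as possible about all possible AESIs". SAP 6.1 (Safety endpoints) has the study physician compile narratives for possible SAEs and AESIs, but of these "Events possibly linked to TB-IRIS were presented to an independent expert clinical committee for adjudication". It does not say who judges the possible link.

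Neither document gives a fixed list of recorded events that must go to the committee. Comparing AESIs between arms is a secondary objective (Protocol 3.1.2, SAP 2.2). The analysis is descriptive (Protocol 9.2.2, SAP 6.2).

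**The concern.** Blinded adjudication protects the classification of cases that arrive. It does nothing for cases that were never sent. If people who know the arm suspect TB-IRIS more readily in one arm, the counts differ even when every committee decision is correct.

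Suspicion is a soft judgement in this population. Everyone enters with at least one of cough, fever, night sweats or weight loss (Protocol 5.3.1), and two minor criteria, for example worsening constitutional and respiratory symptoms, satisfy the clinical part of the paradoxical definition (7.1.3). Whether such a symptom is new, worse or IRIS-related is where knowledge of the arm can act. An entry judged not to be a possible event need not leave a record in the trial database, so unequal selection could not be seen at analysis.

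The protocol's own risk assessment names IRIS as the risk of the intervention arm: "the risk of IRIS is increased due to the earlier initiation of ART" (11.2). With rare events and no model, readers will compare raw counts by arm. Over-suspicion in ART first would overstate that harm, and under-suspicion would hide it.

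**Working it through.** **1. The plan's own figure.** The documents give no AESI rate, AESI power or referral sensitivity. The only related figure is 295 per arm for the primary endpoint (Protocol 9.1). It reproduces: n = (1.96 + 0.8416)² × 2 × 0.75 × 0.25 / 0.10² = 7.849 × 0.375 / 0.01 = 294.3, rounded up to 295. The present point does not affect it. It serves below only as the denominator.

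**2. Formula.** Let p be the true AESI risk in an arm and s the probability that a true case reaches the committee. With perfect adjudication, the observed risk is p × s, so

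observed ratio = (true ratio) × (s in ART first / s in TB results first).

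The distortion of the ratio does not depend on the event rate.

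**3. Illustration.** All risks and sensitivities here are assumptions. Expected recorded events are 295 × p × s.

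| True risk, ART first v TB results first | Referral | Recorded events | True ratio | Observed ratio |
|---|---|---|---|---|
| 3% v 3% | 90% v 90% | 8.0 v 8.0 | 1.00 | 1.00 |
| 3% v 3% | 90% v 80% | 8.0 v 7.1 | 1.00 | 1.125 |
| 3% v 3% | 90% v 60% | 8.0 v 5.3 | 1.00 | 1.50 |
| 3% v 3% | 60% v 90% | 5.3 v 8.0 | 1.00 | 0.67 |
| 6% v 3% | 60% v 90% | 10.6 v 8.0 | 2.00 | 1.33 |
| 6% v 3% | 45% v 90% | 8.0 v 8.0 | 2.00 | 1.00 |

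The absolute distortion does depend on the rate. At 90% v 60% referral with no true difference it is p × 0.30: 0.6 percentage points at a true risk of 2%, 1.5 at 5% and 3.0 at 10%.

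**4. Set against chance.** For 8 v 5 events of 295 each, the ratio is 1.6. The standard error of its log is √(1/8 + 1/5 − 2/295) = 0.564, so the 95% interval runs from 1.6 / e^(1.96 × 0.564) to 1.6 × e^(1.96 × 0.564), about 0.5 to 4.8. Chance is larger than the illustrated bias. Bias differs in that it is not covered by the interval.

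**5. Which events are exposed.** An event that leads to death or hospitalisation is an SAE whatever its suspected cause (Protocol 7.1.1). SAEs are also asked about at the week 26 visit and at tracing, whereas AESIs are not (7.1.4). A serious IRIS event is therefore likely to be on record, and what can go wrong is that it is never put forward as IRIS. A non-serious IRIS event can be missed altogether.

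**The case against.** The case against has real weight.

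- **Register review.** It is mandatory in both arms, covers all entries, names AESIs at day 28 and closes with a check at week 30 (Protocol 6.7, 6.8, 6.10). Published case criteria apply. This stands as a limit on the problem. It ensures that entries are read, not that they are judged without knowledge of the arm. SAP 6.1 also omits register review as an AESI route, whereas Protocol 7.1.4 includes it.
- **Consequence.** Mortality and SAEs are captured separately and the DSMB reviews SAEs. AESIs are only described. This also stands: no test and no non-inferiority conclusion changes, and the safety reading does not rest on AESIs alone.
- **Magnitude.** No document supports any particular gap in referral. This stands too, and the figures above are illustrations only.
- **Timing.** SAP version 2.0 is dated January 2025 and reports presentation to the committee in the past tense, so prospective capture cannot be changed. What remains is selection from data already held, and reporting.

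A reader might make two stronger inferences that the documents do not support. The first is that routine staff are told to expect more IRIS in ART first. That statement is in the ethics section (11.2), which also gives the opposing risk and calls the balance unclear. Protocol 6.8 says only that staff are trained to recognise SAEs and AESIs. The second is that the study physician or National PI can veto a case. Protocol 6.8 lets them decide on further assessment and documentation, not explicitly on whether a case goes to the committee.

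**Conclusion.** The point holds as a limited weakness of a descriptive safety comparison, and it should be addressed. Routine staff and site investigators know the arm and decide what counts as a possible AESI. The SAP then sends only events possibly linked to TB-IRIS to the committee, and no arm-neutral selection rule exists. Bias can follow even with perfect adjudication. Its direction and size cannot be determined from the documents: under the assumed referral patterns, a true ratio of 1.0 appears as anything from 0.67 to 1.5, and a true ratio of 2.0 as 1.33 or 1.0.

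The exposure is mainly to AESI classification and to non-serious IRIS. The sample size and the primary non-inferiority test are untouched. The conclusion rests on the absence of any fixed selection rule in the protocol or SAP. A rule held in a separate committee document would narrow the point.

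**What to change.** By addendum to SAP 6.1, add a fixed selection rule, run identically in both arms on data already held. In addition to any event staff flagged, send to the blinded committee:

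- every SAE or death with onset within 3 months after ART (re)start, the period used in the protocol's own TB-IRIS definition;
- every TB diagnosis recorded in the database within that period.

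Report by arm the numbers that met the rule, were flagged by staff, were adjudicated and were confirmed. A gap between rule-selected and staff-flagged cases that differs by arm would make unequal suspicion visible.

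Do not add a trigger based on complaint visits. Visits that staff did not regard as a possible SAE or AESI need not be in the database (Protocol 6.8), so such a rule would largely return what was already flagged unless clinic registers at the 11 sites were abstracted again.

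State as a limitation that non-serious events still depend on unblinded ascertainment. So do clinical TB diagnoses, because SAP 6.1 accepts the responsible provider's judgement and routine staff know the arm.

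The cost is SAP wording and more dossiers for the existing committee. If 5% to 10% of 590 participants met the rule (an assumption), that is about 30 to 60 dossiers. The SAP already calls for narratives on possible SAEs and AESIs; TB diagnoses not flagged as either may need a short summary. No new visits or tests are required.

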## 6.12 Schedule of events

TIMEPOINT	0 Screening enrolment	TB results	28 days Register review	Week 26 (22-30) Study visit	30 week Register review	Weeks 31-40 Tracing 
Eligibility screening	X					
Arm allocation	X					
INTERVENTION:						
ART initiation ("ART first arm")	X					
ART initiation ("TB results first arm")		X 				
ASSESSMENTS:						
Questionnaire (including brief medical history)	X			X		(X)
Brief physical examination	X			X		(X)
CD4 cell count	X					
CrAg test if CD4 <200 cells/ml or clinical indication	X					
TB investigations 	X					
Collection of plasma samples 	X			X		(X)
SAE and AESI surveillance 	(X)	(X)		(X)		
HIV Viral Load				X		(X)
Register review: Ensure complete and correct trial data by checking routine registers			X		X	
ROUTINE CARE:						
ART counselling	X	X		X		
ART refills 				X		(X)
Start TB treatment or TPT 		X				
Ongoing clinical care as required	(X)	(X)		(X)		(X)
Start CPT 	(X)					

Tracing via phone calls and home visits if no documented VL in endpoint assessment window at 22-30 weeks

 ART provision by routine services, the trial intervention is to allocate the timing of ART

 ART start if not diagnosed with TB disease, if TB disease diagnosed ART may be delayed up to 14 days— according to local routine

 According to local routine

 Or DBS if venous blood draw is not possible

 AE surveillance; participants, family members and routine staff are asked to contact study team in case of medical complaints. Referral to study team for in case of suspected SAE or TB-IRIS

 According to local routines

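### The masked TB-IRIS committee is shown the local physician's own judgement, which weakens, but does not remove, the masking of the AESI endpoint

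*Protocol*

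**What the plan says.** An adverse event of special interest (AESI) is an event consistent with TB-IRIS in the view of an independent clinical committee (Protocol 7.1.1). That committee's judgement therefore defines the endpoint.

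On masking, Protocol 4.2.2 states: "For the endpoint assessment of AESI incidence, an expert panel will review clinical data, blinded to arm allocation". Protocol 7.1.3 repeats it: "The adjudication committee will be blinded to arm allocation". SAP 6.1 (Safety endpoints) says the same.

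On what the committee sees, Protocol 7.1.3 first lists the facts to be collected: "Information will be gathered about TB diagnoses, timing of ART initiation (relative to TB diagnosis and treatment), clinical course", together with alternative explanations. It then says: "This information (including judgement of study physician, National PI or delegate) will be presented to an independent expert clinical committee". SAP 6.1 describes a narrative report compiled by the study physician, "including judgment of study physician, National PI or delegate".

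On who else is masked, Protocol 4.2.2 says: "It is not feasible to blind participants and site investigators to arm allocation". The only parties it describes as blinded are the laboratory staff who process viral loads and the expert panel.

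Neither document describes redacting the narrative, withholding the local opinion, or checking that masking held.

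**The concern.** Masked adjudication is the plan's stated protection for the AESI comparison. It works to the extent that the committee reaches its view from facts that do not carry the arm. An opinion from someone who knows the arm is a different kind of input: removing the allocation label from the file does not remove the label's influence on a conclusion already drawn.

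Two features make this relevant here. First, the expectation has a direction: Protocol 11.2 says the risk of IRIS is raised in the ART-first arm because ART starts earlier. Second, the case definition leaves room for judgement. Unmasking TB-IRIS can rest on the intensity of the presentation, and for paradoxical TB-IRIS alternative explanations are to be ruled out only where that can be done (Protocol 7.1.3). At stake is the between-arm description of the main harm the protocol expects from same-day ART.

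**Working it through.** **The plan's own figure.** The documents give no rate for TB-IRIS and no figure for adjudication. The only relevant number is the arm size in Protocol 9.1: suppression 75% in both arms, margin 10%, one-sided alpha 0.025, power 80%.

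n per arm = (z_0.975 + z_0.80)² × [p₁(1 − p₁) + p₂(1 − p₂)] / margin²

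= (1.960 + 0.842)² × (0.1875 + 0.1875) / 0.10² ≈ 7.849 × 0.375 / 0.01 ≈ 294.3, rounded up to 295 per arm, 590 in total.

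This matches the stated 295 and 590. The present point does not affect it.

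**Does the local opinion reach the committee?** Yes. Protocol 7.1.3 and SAP 6.1 both include it. Neither spells out what the judgement is about; since it accompanies a possible AESI, the natural reading is whether the event is TB-IRIS.

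**Do those giving the opinion know the arm?** Neither document says so outright. Three facts point that way:
- The trial is open-label, and Protocol 4.2.2 blinds no clinical role outside the panel.
- Under Protocol 7.1.6 the study physician or National PI makes the first causality assessment of SAEs and reports by relatedness to the study intervention, which is hard to do without knowing the arm.
- Under Protocol 6.8 the same people review what the unblinded site investigators submit and decide whether more documentation is needed.

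Knowledge of arm is thus a strong inference.

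**Does ART timing give the arm away regardless?** Only in part. A footnote to Protocol 6.12 says "ART provision by routine services, the trial intervention is to allocate the timing of ART", and the case definitions need ART timing. But they need it relative to TB diagnosis, TB treatment and symptom onset, whereas the arms differ in ART timing relative to enrolment and completion of the TB work-up. The sequences can overlap:
- A TB-results-first participant with a negative work-up then starts ART (Protocol 6.6.1 and 6.6.2). If TB appears later, the order is ART then TB, as it would be in the ART-first arm.
- A TB-results-first participant diagnosed with TB on the enrolment day may start ART that same day (Protocol 6.4.1), which is also when ART is offered in the other arm.

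In such cases dates counted from ART start, without the enrolment date, preserve real masking. Where ART starts shortly before the result of the enrolment TB work-up, the timing still suggests the arm.

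**Scale, as illustration only.** One reclassified event in an arm of 295 is 1/295 = 0.3 percentage points; three are 3/295 = 1.0 percentage point. The count of three has no basis in the documents.

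**The case against.** The strongest reply is that the committee is masked, as both documents say, and that an opinion does not disclose allocation. Nothing states that the local judgement names or implies the arm. This stands: the problem is possible influence on masked readers, not absent masking.

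A second reply is that the opinion is useful evidence. Many events are reconstructed from registers, staff and phone calls (Protocol 6.8), and the criteria ask readers to consider drug resistance, adherence, other infections and toxicity. This stands for the facts the physician found. It is weaker for the physician's conclusion, which can be shown after the committee has recorded its own.

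A third reply is that removing the opinion leaves other routes open. ART timing stays in the file. Case selection also happens upstream: the local physician or National PI decides on further documentation, and SAP 6.1 says that events possibly linked to TB-IRIS were the ones presented. This stands as a limit on what the fix achieves.

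Finally, the consequence is limited. AESIs are secondary and summarised descriptively, with no test or decision rule (Protocol 9.2.2, SAP 6.2). The primary endpoint is a viral load processed by blinded laboratory staff.

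**Conclusion.** The point holds as a weakness in masking that is cheap to reduce. The committee does not see the label, but the plan exposes it to an opinion very probably formed with the arm known, in a setting where the protocol itself expects more IRIS in one arm. Reporting the adjudication simply as blinded would overstate the protection.

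This rests on two assumptions: that the study physician, National PI or delegate knows the arm, and that no separate committee procedure, not described in either document, already withholds the opinion.

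A reader might infer more: that the AESI endpoint has no protection from knowledge of arm, or that the committee is handed the enrolment date or an arm label. The documents do not support this. They state that the committee is blinded, and neither places those items in the case material. The narrative draws on all available facility records, so an enrolment date could appear in it, but that is not stated.

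The size and even the presence of bias cannot be estimated from the documents. The primary analysis and the sample size are unaffected.

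**What to change.** In Protocol 7.1.3 and SAP 6.1 (Safety endpoints), or in the committee's working procedure:

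- Keep the factual narrative, including findings on alternative explanations, but withhold the local opinion on whether the event is TB-IRIS until the committee has recorded its classification.
- Give ART, TB and symptom dates as days relative to ART start, and leave out the enrolment date.

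SAP version 2.0 is dated 14 January 2025, the synopsis planned last participant out for December 2024, and SAP 6.1 refers to presentation of events in the past tense. Some adjudication may therefore be complete. If it was done with the opinion visible, an amendment cannot change it; the trial report should then say that adjudicators saw the local opinion and ART timing and that masking was partial.

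The cost is light editing of what should be a small number of files, since the SAP expects these events to be rare, or a sentence in the report. The downside is slightly less context for sparsely documented events. ART timing relative to TB diagnosis can still suggest the arm in some cases, so the change does not restore full masking. No case definition, sample size or clinical care changes.
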